Clinical management and medication treatment	
The ongoing management and treatment of patients in the study group, as well as those withdrawn from the study following the ESC, ESC/ESH, ESC/EACTS, ESC/ESVS, ACC/AHA, ACC/AHA/ASA, ACG, ISTH guidelines and recommendations for CAD and concomitant ASCVDs.
 
Treatment of other concomitant diseases/conditions following the recommendations provided by national protocols and guidelines, and taking into account the contraindications and limitations of the use of individual medications.

Primary clinical end-points for outcome measures	
 
— Death from any cause within a 12-month of the study follow-up;
 
— Death from any cardiovascular cause within a 12-month of the study follow-up;
 

Secondary clinical end-points of outcome measures	
 
— Non-fatal myocardial infarction within a 12-month of the study follow-up;
 
— Unstable angina or angina requiring hospitalization within a 12-month of the study follow-up;
 
— Stroke or transitory cerebral ischemic event within the study follow-up period within a 12-month of the study follow-up;
 
— Major bleeding within a 12-month of the study follow-up;
 
— Non-major bleeding within a 12-month of the study follow-up;
 
— Heart failure event within a 12-month of the study follow-up;
 
— Percutaneous coronary intervention or coronary artery bypass-grafting within a 12-month of the study follow-up
 

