Other end-points of outcome measures	
 
— Composite of death from any cause, non-fatal myocardial infarction, stroke, or major bleeding within a 12-month of the study follow-up (Net adverse clinical events - NACEs);
 
— Composite of death from any cause, non-fatal myocardial infarction, or stroke within a 12-month of study follow-up (Major adverse cardio or cerebrovascular events - MACCEs);
 
— Composite of death from cardiovascular cause, non-fatal myocardial infarction, recurrent angina, or repeated revascularization (PCI or CABG) within a 12-month of study follow-up (Major adverse cardiovascular events - MACEs);
 
— Number of study participants whose health status was defined as good or satisfactory, or with the appearance of CVD symptoms, or with a significant inability to self-care (Patient-Reported Health Status) reported by the patient or patient caregiver at 3, 6 and 12 months of the study follow-up;
 
— Participants self-reported (or patient's caregiver reported) angina not required hospitalization (Patient-Reported Angina Not Required Hospitalization at 3, 6 and 12 months of the study follow-up;
 
— Participants reported (or patient's caregiver reported) last week's shortness of breath due to heart failure not requiring hospitalization (Patient-Reported Heart Failure Severity) at 3, 6 and 12 months of the study follow-up;
 
— Withdrawal for any reason within a 12-month of the study follow-up;
 
— Costs of clinical service utilization for case management during the study follow-up;
 
— Incremental costs incurred for real-world health care services, including costs for the MACCEs, MACEs and NACEs;
 

Other measures	
 
— Cardiometabolic risk factors and their control status;
 
— Total number of hospitalizations for any reason within 12 months of the study follow-up;
 
— Comorbidities;
 

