#### **2.5.4 Disclosure of Study Results**

The allocation of patients to the experimental and control groups will be carried out by double-blind randomization. At this stage, the results of the randomization will be hidden from the study participants, the medical care team, and the clinical outcome assessors. However, after randomization and CYP2C19 genotyping, the results will be disclosed to the study participants and the medical care team, and the results of both the baseline and ongoing clinical assessments of the study subject will be known throughout the study.

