## **2.6 Evaluation of Study Results**

### **2.6.1 Study Endpoints**

The study follow-up results will be discussed and presented by study arms, as well as concerning the primary and secondary endpoints of the study.

The study results will also be discussed concerning other endpoints, which will be represented by clinical or non-clinical data and characterize the factors that affect the efficacy of antiplatelet treatment and determine the clinical and non-clinical outcome in the course of the CCSs both with and without the results of CYP2C19 genotyping.

The indicators for assessing the effectiveness of the study are presented in Appendix 5.

In the study, the selection of treatment regimens with clopidogrel and an alternative P2Y12 inhibitor will be carried out by determining the genotype of the CYP2C19 \*2, \*3 non-functional alleles. Clopidogrel will be used in study participants with CYP2C19 \*2, \*3 normal allele genotypes and in the control arm of study participants not undergone CYP2C19 genotyping – unspecified CYP2C19 genotype. Study participants with CYP2C19 \*2, \*3 non-functional allele genotypes will be given alternative antiplatelet therapy.

In cases of CAD, regardless of treatment with P2Y12 inhibitors after ePCI, the clinical endpoints will be represented with MACCEs and other clinical conditions related to CAD or the potential adverse events of antiplatelet drug treatment. The incidence of the primary, secondary and other study endpoints defined as clinical outcomes of CYP2C19 genotype-guided P2Y12 inhibitor treatment will be assessed in the study arms.

The primary endpoints of the study are defined as:

- Number of study participants who died from any cause (Death from Any Cause) within a 12-month of the study follow-up;
- Number of study participants who died from any cardiovascular cause (Death from Cardiovascular Cause) within a 12-month of the study follow-up;

The secondary endpoints of the study are defined as:

- Number of study participants who experienced non-fatal myocardial infarction (Non-fatal Myocardial Infarction) within a 12-month of the study follow-up;
- Number of study participants who experienced unstable angina or angina requiring hospitalization (Unstable Angina) within a 12-month of the study follow-up;
- Number of study participants who experienced a stroke or transitory cerebral ischemic event (Stroke or TIA) within a 12-month of the study follow-up;

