- Number of study participants who experienced major bleeding (Major Bleeding) within a 12-month of the study follow-up;

- Number of study participants who experienced non-major bleeding (Non-major Bleeding) within a 12-month of the study follow-up;
- Number of study participants who experienced a heart failure event (Heart Failure Event) within a 12-month of the study follow-up;
- Number of study participants who experienced percutaneous coronary intervention or coronary artery bypass-grafting (Repeated Coronary Revascularization) within a 12-month of the study follow-up;

Pre-specified endpoints of the study are defined as:

- Number of study cases in each arm with a composite of death from any cause, myocardial infarction, stroke, or major bleeding (Net adverse clinical events - NACEs) within a 12-month of the study follow-up;
- Number of study cases in each study arm with a composite of death from any cause, myocardial infarction, or stroke (Major adverse cardiac or cerebral events - MACCEs) within a 12-month of the study follow-up;
- Number of study participants who reported their health status as good or satisfactory, or with the appearance of CVD symptoms, or with a significant inability to self-care (Patient-Reported Health Status) at 3, 6 and 12 months of the study follow-up;
- Number of study participants self-reported angina not required hospitalization (Patient-Reported Angina Not Required Hospitalization) at 3, 6 and 12 months of the study follow-up;
- Number of study participants reported last week's shortness of breath due to heart failure not requiring hospitalization (Patient-Reported Heart failure Severity) at 3, 6 and 12 months of the study follow-up;
- Number of study participants withdrawn from the study for any reason within a 12-month of the study follow-up;
- Costs of clinical service utilization for case management during the study follow-up;
- Costs incurred for incremental services, including costs for the major adverse cardiovascular and cerebrovascular event;

Along with studying the effectiveness of CYP2C19 genotype-guided treatment selection with clopidogrel and an alternative P2Y12 inhibitor, clinical case management processes in the real-life healthcare system and factors that positively and negatively impact the processes will be evaluated: healthcare processes, place of care, delivery of medical procedures, medication use, and management of comorbidities.

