The absolute benefit (AB) of CYP2C19 *2, *3 genotype-guiding clopidogrel treatment application for avoiding MACCE	Calculating: The absolute benefit (%) = the rate (%) of MACCE among 'unspecified metabolizer' study participants – the rate (%) of MACCE among 'normal metabolizer' study participants
The absolute benefit (AB) of CYP2C19 *2, *3 genotype-guiding any P2Y12 inhibitor antiplatelet treatment application for avoiding MACCE	Calculating: The absolute benefit (%) = the rate (%) of MACCE among 'unspecified metabolizer' study participants – the rate (%) of MACCE among aggregated 'normal metabolizer' and 'passive metabolizer' study participants
The rate (percentage - %) of recurrent angina among study participants	Numerator: Number of study participants with recurrent angina Denominator: Total number of study participants

The rate (percentage - %) of recurrent angina among 'normal metabolizer' study participants	Numerator: Number of 'normal metabolizer' study participants with recurrent angina Denominator: Total number of 'normal metabolizer' study participants
The rate (percentage - %) of recurrent angina among 'passive metabolizer' study participants	Numerator: Number of 'passive metabolizer' study participants with recurrent angina Denominator: Total number of 'passive metabolizer' study participants
The rate (percentage - %) of recurrent angina among 'unspecified metabolizer' study participants	Numerator: Number of 'unspecified metabolizer' study participants with recurrent angina Denominator: Total number of 'unspecified metabolizer' study participants
The hazard ratio (HR) of recurrent angina for 'normal metabolizer' study participants vs 'unspecified metabolizer' study participants	Numerator: the hazard rate from recurrent angina of 'normal metabolizer' study participants, calculated as the proportion of recurrent angina among 'normal metabolizer' study participants Denominator: the hazard rate from recurrent angina of 'unspecified metabolizer' study participants, calculated as the proportion of recurrent angina among 'unspecified metabolizer' study participants

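### MACE and the Appendix 3 angina rows use 'recurrent angina', an undefined term that matches neither listed angina endpoint, and MACE also counts revascularisation planned before randomisation

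*Combined protocol and SAP*

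**What the plan says.** The plan has two angina endpoints. The secondary one, in the Synopsis, is "Unstable angina or angina requiring hospitalization within a 12-month of the study follow-up"; Section 2.6.1 words it as "Number of study participants who experienced unstable angina or angina requiring hospitalization (Unstable Angina"). The other, assessed at 3, 6 and 12 months, is "Number of study participants self-reported angina not required hospitalization (Patient-Reported Angina Not Required Hospitalization").

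The Synopsis then lists MACE among the other endpoints, as "Composite of death from cardiovascular cause, non-fatal myocardial infarction, recurrent angina, or repeated revascularization (PCI or CABG"). Section 2.6.1 does not list MACE; the only composites there are NACE and MACCE.

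Appendix 3 tabulates angina only under the MACE term. The overall numerator is "Number of study participants with recurrent angina", and the arm-specific rows follow suit, for example "Number of 'unspecified metabolizer' study participants with recurrent angina". It has no rows for unstable or hospitalised angina, and none for patient-reported angina.

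Sections 2.5.8, 3.1 and 3.2.1 name recurrent angina among the MACCEs, and 3.2.1 calls MACCE a study clinical endpoint. The MACCE composite in the Synopsis and Section 2.6.1 (death, MI, stroke) has no angina component.

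On masking, Section 2.5.4 says that after randomisation and genotyping "the results will be disclosed to the study participants and the medical care team".

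The revascularisation endpoint is "Number of study participants who experienced percutaneous coronary intervention or coronary artery bypass-grafting (Repeated Coronary Revascularization") within 12 months, with no exception for procedures already planned at entry.

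**The concern.** A composite in an open-label trial needs components that two sites would code the same way. Recurrent angina has no criterion for severity, hospitalisation or objective ischaemia, and no adjudication is described. One site could count a complaint voiced at a 3-month visit and another could count only admissions, and both would comply. The person who reports the symptom knows the genotype result, or knows that no test was done.

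MACE has a full set of rate, HR, RR and benefit rows in Appendix 3 and its own cost comparisons. The Synopsis allows effectiveness indicators to be selected after the results have been reviewed, so a soft composite could end up prominent in the report.

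The revascularisation component raises a separate issue. Participants may enter within 12 weeks of an elective PCI, and Section 2.5.1 records the number of obstructive lesion sites. If a second-stage procedure had been decided before randomisation, it would be counted as an outcome that assignment could not have influenced.

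**Working it through.** The plan gives no figure for angina or MACE to reproduce. Its sample-size inputs (0.4 versus 0.6) name no endpoint. The only frequency for an event class that includes recurrent angina is the 1 to 10% given for MACCEs in Section 3.2.1.

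**Step 1. The terms side by side.**

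| Place | Angina term |
|---|---|
| Synopsis and 2.6.1, secondary endpoint | unstable or hospitalised |
| Synopsis and 2.6.1, other endpoint | self-reported, not hospitalised |
| Synopsis, MACE | recurrent |
| Appendix 3 | recurrent |
| 2.5.8, 3.1 and 3.2.1, MACCE lists | recurrent |
| Synopsis and 2.6.1, MACCE composite | none |

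The third term is neither of the first two, and no section links them.

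**Step 2. Sensitivity to reporting, no true effect.** Assumed: cardiovascular death, MI and revascularisation together 6%; self-reported angina s, independent of these; reporting lower by a quarter in one arm.

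- MACE = 1 − 0.94 × (1 − s)
- Share from self-report alone = 1 − 0.06/MACE
- MACE with less reporting = 1 − 0.94 × (1 − 0.75s)
- RR = MACE with less reporting / MACE

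| s | MACE | Self-report only | MACE, less reporting | RR |
|---|---|---|---|---|
| 1% | 6.9% | 14% | 6.7% | 0.97 |
| 5% | 10.7% | 44% | 9.5% | 0.89 |
| 10% | 15.4% | 61% | 13.1% | 0.85 |
| 20% | 24.8% | 76% | 20.1% | 0.81 |
| 25% | 29.5% | 80% | 23.6% | 0.80 |

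If disclosure raised reporting by a quarter instead, replacing 0.75s with 1.25s gives RR 1.03, 1.11, 1.15, 1.19 and 1.20.

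**Step 3. Chance of a false-positive MACE result.** This uses 160 guided versus 80 control and a two-sided 0.05 test of two proportions (normal approximation). Assumed: no true effect, other components 1 to 10%, reported angina 10 to 20% in the guided group. Equal reporting gives 5%. If control participants report 5 points more angina, the chance is 12 to 21%; at 10 points more it is 30 to 54%. For example, with other components at 5% and angina at 10% versus 15%, MACE is 1 − 0.95 × 0.90 = 14.5% versus 1 − 0.95 × 0.85 = 19.3%, and the chance of rejection is 17%.

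**Step 4. Dilution.** Suppose a component unrelated to treatment occurs equally in both groups, as planned procedures should on average. Assume a true halving of the other events from 10% to 5%. With the unrelated component at 10%, RR = (1 − 0.95 × 0.90)/(1 − 0.90 × 0.90) = 0.145/0.190 = 0.76. At 20%, RR = 0.240/0.280 = 0.86. Power with 160 versus 80 falls from 33% to 16% and 11% respectively. The documents do not say how often staged procedures occur, so the size of this effect in the trial is unknown.

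**The case against.** Much of the case on the other side stands.

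- **Does self-report count?** The plan lists self-reported angina separately, just below MACE. Section 3.2.1 describes MACCEs as severe and clinically serious. Sections 3.2.6 and 3.3 end planned follow-up after a MACCE; if every self-reported episode qualified, participants would leave at the first report and the angina question at 3, 6 and 12 months would make little sense. So the text leans toward a narrower meaning, but it does not state one.
- **Is the secondary endpoint unreported?** A reader might infer that hospitalised angina gets no result. The documents do not support that. Section 2.5.7 commits to determining the incidence of every primary, secondary and other clinical endpoint, Section 2.6.1 to presenting results by arm and endpoint, and Section 2.6.3 to effect measures for clinical endpoints. The gap is in Appendix 3's comparison rows.
- **Do staged procedures bias MACE?** A reader might infer this too. Procedures planned before randomisation should balance between the guided and control groups on average, so they dilute the randomised comparison. The documents never mention staged procedures, and Section 2.5.1 does not say that untreated lesions remain.
- **Who is unmasked?** Section 2.5.4 names participants and the care team for disclosure after randomisation. It does not say that outcome assessors are unmasked. The reporter of self-reported angina is.
- **How much depends on MACE?** It is an 'other' endpoint, and angina reporting does not touch either primary endpoint.

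**Conclusion.** The definitional defect holds. MACE and Appendix 3 rest on an undefined angina term that matches neither listed angina endpoint, and Section 3.2.1 places the same term inside a MACCE whose composite definition excludes it. In an open-label setting this permits, but does not prescribe, the counting of self-reported angina in MACE.

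It might be inferred that self-report would supply most MACE cases. That requires angina rates that the documents do not give: the share is 61 to 80% at an assumed 10 to 25%, but only 14 to 44% at 1 to 5%. The null relative risk ranges from about 0.97 to 0.80 under an assumed 25% drop in reporting. Its direction is also open, because the guided group contains both people told that they are normal metabolizers and people told that they carry loss-of-function alleles.

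The revascularisation component adds dilution of unknown size. The change should be made because it is cheap and removes an ambiguity. It does not threaten the primary analysis of death.

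**What to change.** 1. In the Synopsis MACE definition and the Appendix 3 angina rows, replace recurrent angina with the existing secondary endpoint of unstable or hospitalised angina. This also supplies the missing comparison rows.
2. Keep self-reported angina without hospitalisation as its own endpoint, outside MACE.
3. Reconcile the MACCE list in Section 3.2.1 with the MACE and MACCE definitions in the Synopsis and Section 2.6.1. Sections 3.2.6 and 3.3 attach the end of participation to a MACCE, so they must be read together with that list and with the 12-month endpoints.
4. For the revascularisation endpoint and the MACE component, do not count a procedure documented as planned before randomisation. Record this at baseline.

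The cost is a wording change in the endpoint list and Appendix 3, one yes/no field, and fewer MACE events. Defining recurrent angina objectively would also remove the ambiguity. Using the existing endpoint is simpler because the trial already collects it. No visit or treatment changes.

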## 2.5 Study Procedures

### 2.5.1 Screening

All patients

- must present having undergone ePCI within the past 12 weeks, documented by imaging and a report form,

[or]

- a practical clinical task must be defined to de-escalate antiplatelet therapy from an alternative P2Y12 inhibitor to clopidogrel or initiate clopidogrel.

eICA data must meet the criteria for CAD, and ePCI results must determine the indication for treatment with clopidogrel or an alternative P2Y12 inhibitor:

- Coronary artery stenosis;

[and]

- Coronary artery stenting with DES;

Study subjects must have formally confirmed informed consent to participate in the study, as approved by the ethics committee.

Study subjects should undergo baseline clinical assessments that will determine:

- Demography data:
  - Sex; Age; Race, Ethnicity, Country of residence.
- Cardiometabolic risk factors and their control status:
  - BMI; Obesity; Systolic and Diastolic Blood Pressure, Hypertension; T2 Diabetes Mellitus; HbA1c Measures; LDL-C, Dyslipidemia;
- History of Cardiovascular Morbidity. The patient must undergo all clinical-diagnostic examinations that confirm inclusion criteria and deny exclusion criteria:
  - Clinical indications for the most recent PCI;

- Angina
- No Angina: Heart Failure Event, Supraventricular Tachycardia, Atrial Fibrillation, Premature Ventricular Complex or Ventricular tachycardia, Left Bundle Branch Block;
- Other non-specific symptoms;
- History of any Cardiovascular Morbidity and their control status:
  - Prior Myocardium Infarction, Number of Prior MIs; Chronic Heart Failure; Supraventricular Tachycardia; Atrial Fibrillation; Premature Ventricular Complex; Ventricular Tachycardia; Ventricular Fibrillation Event; Sinus Node Dysfunction; AV Block; Left Bundle Branch Block; Right Bundle Branch Block; Coronary artery bypass graft;
- History of prior PCI:
  - Number of prior PCIs; Number of Coronary Artery Lesion Sites – total and obstructive; Number of Stents Ever Placed; Sites of Coronary Artery Lesions – obstructive and non-obstructive
- History of Co-morbid Diseases/Conditions and their control status. The patient must undergo all clinical-diagnostic examinations that confirm inclusion criteria and deny exclusion criteria:
  - Peripheral Artery Disease; Carotid Artery Disease; Cerebrovascular Disease;
  - Other co-morbid diseases/conditions:

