## **2.5.7 Efficiency Assessment**

The efficiency of the study is assessed based on the results of investigational product application, the CYP2C19 genotype-guided preventive treatment with P2Y12 inhibitor and the effectiveness of application of study procedures in real-world clinical practice.

At the 3rd, 6th and 12th months of follow-up, the incidence of the study's primary, secondary and other clinical endpoints (see Chapter 2.6.1 Study Endpoints) will be determined. At the final evaluation, quantitative calculations of their frequency and risk-adjusted clinical outcomes will be performed in the experimental treatment intervention and control arms of the study. Odds Ratio (OR), Relative Risk (RR), Relative Benefit (RB), and Absolute Benefit (AB) indicators will be determined. The efficacy of the study product will be evaluated by considering by evaluation study indicators presented in Appendix 2. Measuring more than three-fourths (>75%) of these indicators will consider the efficiency of the study.

Biases in the study and related evaluations will be avoided by random selection of study participants for intervention and control arms and by excluding confounder variables from the statistical analysis. See study participants' selection procedures in Chapter 2.3.2, Structural Design.

After randomization of the study participants will be allocated into experimental and control arms. 2 experimental arms will be formed based on the results of CYP2C19 genotyping results, one of which will be used as a parallel control group as well. Each arm of the study participants will differ from each other according to the principal characteristic, which is determined by the results of CYP2C19 genotyping, and treatment with a P2Y12 inhibitor will be selected based on the results of CYP2C19 genotyping:

- Clopidogrel treatment in patients with the genotype of CYP2C19 \*2, \*3 normal alleles, "active metabolizers" - experimental arm;
- Clopidogrel treatment without CYP2C19 genotyping, "Unspecified metabolizers group" - experimental arm;
- Clopidogrel alternative P2Y12 inhibitor treatment group, CYP2C19 \*2, \*3 loss-of-function allele genotype, "passive metabolizers" – comparator (control) arm;

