### **2.6.3 Statistical Analysis of Study Results**

Primary statistical analysis will be carried out using descriptive statistics methods. The values and distribution of quantitative and qualitative variables from the study participants' initial clinical assessment and follow-up results will be evaluated according to the experimental and control arms. The magnitudes and trends of the variations of the data values will be analyzed.

Quantitative variable data will be calculated by mean, standard deviation, and median. For comparative statistical analysis, differences between the variable values will be calculated using the t-test or the Wilcoxon signed-rank test.

Categorical variable data will be calculated as frequencies and percentages (%). For comparative statistical analysis, differences between the variable values will be calculated using the chi-square or Fisher's exact tests.

To analyze the effectiveness of selected study interventions, the frequency of detection of clinical endpoints in the experimental treatment intervention arms (Rt1 and Rt2) and the comparator arm (Rc) will be calculated. According to the frequencies of clinical endpoint-positive and -negative cases detected in the study arm, the odds ratio (OR), hazard ratio - Cox proportional hazards regression (HR), relative risk (RR), relative benefit (RB) and absolute benefit (AB) indicators at 95%CI will be calculated.

The obtained results and indicators of treatment intervention effectiveness will be selected to consider the applicability of the study findings and the possibility of the study results translation into real-world clinical practice.

Data evaluation will be carried out continuously, immediately after they enter the registration form and the database. Preliminary statistical calculations and analysis for study evaluation and monitoring will be provided in several stages, when:

I - More than 50% of patients will be included in the study;

II - The study arms will be fully formed, and more than 50% of patients will complete a 3-month and a 6-month follow-up;

III - All study participants will be included in the study, and at a minimum, half of them will complete a 6-month and a 12-month observation period;

IV - All study participants included in the study will complete a 12-month follow-up.

The development of clinical endpoints will be monitored, and the relevant data will be collected in a special data registration form.

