**Appendix 2. Schedule of Visits to Study Participants Included in the Study**

Research Procedures	Screening	Randomization	3 rd month follow-up	6 th month follow-up	12 th month follow-up	Study withdrawal follow-up
Informed consent to participate in the study	—	✓	—	—	—	—
Medical examination/evaluation	✓	✓	✓	✓	✓	✓
Clinical criteria for CAD	✓	—	—	—	—	—
Inclusion/Exclusion Criteria	✓	—	—	—	—	—
Inherited risks	✓	—	—	—	—	—
Cardiometabolic risks	✓	—	—	—	—	—
Patient medical history	✓	—	—	—	—	—
Hospitalization history	✓	—	—	—	—	—
History of comorbidities	✓	—	—	—	—	—
Outcomes of medical care outside the scope of the study	✓	—	✓	✓	✓	✓
Adherence to medication treatment (BMQ)	✓	—	✓	✓	✓	✓
Data collection and processing procedures	✓	✓	✓	✓	✓	✓
Evaluation of clinical end-points	—	—	✓	✓	✓	✓
CYP2C19 *2, *3 genotyping	—	✓	—	—	—	—
Anthropometry	✓	—	—	—	—	—
Standard 12-lead ECG	✓	—	✓	✓	✓	✓
Doppler-, Echocardiography	✓	—	—	✓	✓	✓
Complete Blood Count (CBC)	✓	—	✓	✓	✓	✓
Glycated Hemoglobin (HbA1c)	✓	—	—	✓	✓	✓
Creatinine, eGFR (MDRD)	✓	—	✓	✓	✓	✓
Study Monitoring Evaluation	✓	✓	✓	✓	✓	✓

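### The three patient-reported outcomes have no screening answer and no longitudinal model, so the planned comparison gives up precision; fixing this is cheap but will not make these outcomes adequately powered

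*Combined protocol and SAP*

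**What the plan says.** The Synopsis lists the three outcomes under other end-points, and section 2.6.1 lists them among the pre-specified ones. All are counts of participants at three follow-up visits: "Patient-Reported Health Status) at 3, 6 and 12 months of the study follow-up", "Patient-Reported Angina Not Required Hospitalization) at 3, 6 and 12 months of the study follow-up", and, for breathlessness in the Synopsis, "Patient-Reported Heart Failure Severity) at 3, 6 and 12 months of the study follow-up".

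In the Appendix 2 schedule, the row "Evaluation of clinical end-points" has a dash at Screening and at Randomization and a tick at months 3, 6, 12 and withdrawal. There is no separate row for patient-reported items.

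Section 2.5.1 introduces the entry data with "Study subjects should undergo baseline clinical assessments that will determine". The list that follows covers demography, risk factors, morbidity, echocardiography and medication. Angina appears under "Clinical indications for the most recent PCI" and chronic heart failure under cardiovascular history. No question put to the patient about current status appears.

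For categorical variables, section 2.6.3 states that "differences between the variable values will be calculated using the chi-square or Fisher's exact tests". Section 2.5.7 begins "At the 3rd, 6th and 12th months of follow-up, the incidence of the study's primary, secondary and other clinical endpoints" and says that these will be determined. It then mentions risk-adjusted outcomes at the final evaluation without naming a model or covariate. Appendix 3 contains no indicator for these three outcomes.

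**The concern.** Symptoms after PCI can be expected to depend on the person's own earlier symptoms, and each person is due to answer three times. A chi-square or Fisher test at a visit uses neither fact.

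One health-status category is the appearance of cardiovascular symptoms. Without the same question at entry, new symptoms cannot be told from symptoms already present. Entry is also mixed: PCI at any time in the last 12 weeks, or a de-escalation decision, with angina, non-angina or non-specific indications. With simple randomisation of 240 people, a chance difference at entry on these items would show only indirectly. No visit is named as the leading one.

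At stake are the precision and interpretation of three lower-tier outcomes. The primary endpoints are deaths and are not touched.

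**Working it through.** **The plan's own figure.** No sample size or power is stated for these outcomes. The 221 in section 2.6.2 reproduces for 0.6 v 0.4 at 1:2, two-sided 0.05 and 80% power (pooled variance in both terms: 74 + 147 = 221). It refers to an unspecified event, so it says nothing about them.

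**Inputs from the documents.** 160 guided and 80 control; about 50 of the 160 are loss-of-function carriers who receive a different drug; 75% expected to complete 12 months (section 2.4.2).

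**Assumptions, not in the documents.** Binary symptom; latent within-person correlation 0.4, 0.6 or 0.8, equal between all visits; symptom rates as given below.

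**Step 1: gain at month 12.** Adjusting for the entry answer multiplies the variance by 1 − φ², where φ is the correlation between the two yes/no answers. At a 25% symptom rate:

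| Latent correlation | φ | 1 − φ² | Effective sample, 1/(1 − φ²) | By simulation |
|---|---|---|---|---|
| 0.4 | 0.240 | 0.942 | ×1.06 | ×1.06 |
| 0.6 | 0.384 | 0.853 | ×1.17 | ×1.18 |
| 0.8 | 0.568 | 0.677 | ×1.48 | ×1.47 |

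**Step 2: visit average.** If the effect is the same at all three visits, the variance factor is (1 + 2φ)/3, or 0.49, 0.59 and 0.71. With the entry answer added it is (1 + 2φ)/3 − φ², or 0.44, 0.44 and 0.39. The condition matters. In simulation with rates of 30% in control and 30%, 24% and 18% in the guided group at months 3, 6 and 12, the unadjusted average had 21–35% power, against 50–58% for month 12 alone.

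**Step 3: what effect is plausible.** At 30% v 18%, simulated power is 50–58% for month 12 alone, 55%, 58% and 68% with the entry answer, and 87–90% for the visit average with the entry answer. If genotyping acts only through the change of drug, a 12-point overall difference needs a fall of 0.12 ÷ (50/160) = 0.384 among those who change. That 38-point fall exceeds the whole 30% assumed for controls.

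Suppose instead that symptoms halve in carriers, from 30% to 15%. The guided rate is then 0.30 − 0.15 × 50/160 = 0.253.

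**Step 4: power at 30% v 25.3%.** The pooled rate is (80 × 0.300 + 160 × 0.253)/240 = 0.269. The standard error is √(0.269 × 0.731 × (1/80 + 1/160)) = 0.0607.
- Single visit: z = 0.0469/0.0607 = 0.77, power about 12%; simulation gives about 11%.
- Visit average with entry answer (factors 0.44 to 0.39): z = 1.16 to 1.24, power 21–24%; simulation gives 20–24%.
- At 60 v 120, after 25% non-completion, the standard error grows by √(240/180) = 1.155. Power is then about 10% for a single visit and 17–19% for the visit average with entry answer.

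Type I error in the complete-data simulations stayed at about 5%. It was not tested under dropout that depends on the outcome.

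**The case against.** The strongest objection is that the benefit is small where it counts. The larger gains belong to the visit average, while month 12 should lead because an effect may appear late. At month 12 the entry answer adds only 3, 6 or 17 points of power even under the optimistic 30% v 18%. This stands.

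Dropout is the second objection. Section 3.2.6 withdraws participants after a MACCE or an anticipated medication effect, and section 3.2.1 counts recurrent angina and heart failure among MACCEs. Whether a self-reported symptom counts is not said. If it does, reporting one ends the series, and missingness depends on the outcome itself. This also stands: three answers per person are not assured, and ordinary GEE would not be safe.

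Third, the plan can be over-read. A reader might infer nine separate p-values per contrast (three outcomes by three visits). Section 2.5.7 says only that incidence is determined at each visit, and section 2.6.3 gives a general rule for categorical data, so the number of tests is not fixed by the text. A reader might also infer that imbalance at entry can be neither seen nor corrected. Section 2.5.1 records angina as PCI indication and chronic heart failure with its control status, which allows a partial check for two of the three outcomes.

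Section 2.3.2 does mention baseline and ongoing assessment of clinical endpoints. It names no patient-reported item and disagrees with the schedule in Appendix 2, so it does not close the gap.

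Finally, treatment is disclosed after randomisation (section 2.5.4). A more precise comparison of self-reported symptoms is also a more precise estimate of any reporting bias.

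**Conclusion.** The point holds as one of efficiency and interpretation. The documents provide no entry answer and no repeated-measures method for these outcomes, and a better analysis is available without extra visits or participants. At month 12 the gain is equivalent to about 6% to 47% more participants, for assumed latent correlations of 0.4 to 0.8. The visit average gains more only if the effect is present at every visit.

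It would be tempting to conclude that the model rescues these outcomes, since 87–90% power appears under 30% v 18%. The documents do not support that reading: with about 50 of 160 guided participants changing drug, such a difference is hardly attainable if genotyping acts only through that change. Under the assumed 30% v 25.3%, power is about 11% for a single visit and 20–24% with the visit average plus baseline, and lower after non-completion. The size of the gain rests on assumed rates and correlations. That nothing is asked at entry and no longitudinal model is named rests on the text alone.

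**What to change.** 1. In Appendix 2, add the same three questions at Screening, before randomisation.
2. In section 2.6.3, specify one longitudinal model per outcome: a binary mixed model (ordinal for health status), or GEE with weighting or imputation for dropout that depends on earlier answers. Include visit, randomised group (guided v control), group-by-visit and the screening answer. Report the month-12 contrast first and the visit average second.
3. For participants already enrolled without a screening answer, adjust angina for angina as PCI indication and breathlessness for chronic heart failure. Health status has no close counterpart in section 2.5.1. If enrolment has closed, items 2 and 3 remain available.
4. State as limitations that the model does not remove reporting bias from disclosed treatment, or informative dropout after withdrawal for a MACCE or an anticipated medication effect, and that power for these outcomes is low.

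The cost is three questions at a visit that already includes a medical examination and the adherence questionnaire, changed forms, a short paragraph in section 2.6.3, and a protocol amendment with IRB approval under section 6.0. The visit average is less sensitive than month 12 if an effect appears late, which is why it comes second.
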